Study Protocol and Statistical Analysis Plan

1. Data Source

This study utilized data from Taiwan's National Health Insurance (NHI) program, a universal health system established in 1996 that covers over 99% of the population. The claims database provides comprehensive and validated medical records for research use. All personal identifiers were encrypted to protect patient privacy. The study protocol was approved by the Institutional Review Board and conducted in accordance with the Declaration of Helsinki.

2. Study Design

A **nested retrospective cohort design** was adopted to evaluate the association between influenza vaccination (IV) and clinical outcomes following fracture-related hospitalizations.

From the nationwide NHI cohort of more than 23 million insured individuals, we identified **561,566 patients aged ≥65 years** admitted for fracture treatment between 2009 and 2020. Among them, **213,381** received IV within 12 months prior to admission, while **348,185** had not.

To reduce confounding, **1:1 propensity score matching (PSM)** was performed between vaccinated and nonvaccinated patients. Matching variables included:

- Demographics: age, sex
- Socioeconomic status (low-income vs. non-low-income)
- Fracture type and comorbidities (within 24 months)
- Emergency visits and hospitalizations during the prior year

3. Outcomes

The **primary outcomes**, assessed within 30 days postadmission, included:

- Pneumonia
- Septicemia
- Urinary tract infection
- Intensive care use
- Hospital length of stay
- Total medical expenditure
- 30-day mortality

Postfracture infections were identified by physician-coded diagnoses during hospitalization or subsequent claims. Patients with pneumonia or septicemia within 6 months before the fracture were excluded.

4. Measures and Definitions

- **Socioeconomic status:** categorized as low-income or non-low-income per NHI copayment exemption criteria.

- **Comorbidities:** identified from 24-month pre-fracture claims using *ICD-9-CM* codes.
- **Postfracture infections:** defined by ICD-9-CM diagnostic codes (listed in Table S1).
- **Influenza vaccine types:** summarized in Table S2.

5. Statistical Analysis

Propensity scores were estimated using **multivariable logistic regression**, including clinically relevant covariates (Table 1). Matching was performed via a **greedy algorithm** with a caliper width of 0.2 SD of the logit of the propensity score.

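### The listed matching variables include no area or hospital variable, so a small bias of unknown direction can enter intensive care use, length of stay and expenditure if uptake and practice both vary by area

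*Combined protocol and SAP*

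**What the plan says.** Section 2 (Study Design) describes a nationwide cohort of "561,566 patients aged ≥65 years", of whom "213,381 received IV within 12 months prior to admission, while 348,185 had not". It states that "1:1 propensity score matching (PSM) was performed between vaccinated and nonvaccinated patients". The listed variables are "Demographics: age, sex", then "Socioeconomic status (low-income vs. non-low-income", then fracture type, comorbidities and the previous year's emergency visits and admissions. Section 4 defines the income item as "categorized as low-income or non-low-income per NHI copayment exemption criteria", which carries no information on location.

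Section 3 (Outcomes) places "Intensive care use", length of stay and "Total medical expenditure" among the seven primary outcomes.

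Section 5 (Statistical Analysis) refers to Table 1 for the covariates in the propensity model. It describes t-tests for continuous variables, chi-square tests for categorical ones, and adjusted odds ratios for infections and mortality. The sensitivity strata are fracture type, sex, age and burden of comorbidity. Region, urbanisation, treating hospital and hospital level are mentioned nowhere in the text.

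**The concern.** Intensive care use, bed-days and cost are measures of resource use. They can reflect how a hospital works (its intensive care capacity and admission policy, discharge habits and cost level) as well as how ill the patient is. If uptake of the vaccine also differs between areas, vaccinated and unvaccinated patients will be spread differently over hospitals. Part of any difference in resource use would then come from place of care.

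Pairing two patients from different areas is not a bias in itself. The problem is a systematic difference between the arms in where patients live or are treated. Nothing in the listed match prevents one. For these three outcomes the match is also the only control of confounding that the text describes, because no adjusted model is named for them. With a cohort of this size, even a small imbalance can give a significant result that reads as a saving, or a cost, due to vaccination.

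**Working it through.** **The plan's own figures.** 213,381 + 348,185 = 561,566, which reproduces the stated cohort; 213,381 / 561,566 = 38.0% vaccinated. With 1:1 matching there can be at most 213,381 pairs. A caliper is applied and the matched number is not given, so this is a ceiling. The documents give no uptake, cost, stay or intensive care data by area. Every input below other than these counts is an assumption.

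**Expenditure.** Assumed inputs: the share treated in higher-cost hospitals differs by 3 to 10 percentage points between arms; those hospitals cost 20 to 30% more; the coefficient of variation (CV) of cost is 1.0 or 1.5; there is no true vaccine effect.

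- Bias relative to the mean of the lower-cost hospitals = imbalance × cost excess.
- Bias relative to the overall mean = that figure / (1 + share × excess). With an assumed half of patients in higher-cost hospitals, the divisor is 1 + 0.5 × 0.20 = 1.10 or 1 + 0.5 × 0.30 = 1.15.
- SE relative to the overall mean = CV × √(2/213,381) = 0.306% at CV 1.0 and 0.459% at CV 1.5. This treats patients as independent, as the t-test does.

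| Imbalance × excess | Bias, lower-cost base | Bias, overall base | z at CV 1.0 (lower-cost / overall base) | z at CV 1.5 (lower-cost / overall base) |
|---|---|---|---|---|
| 0.03 × 0.20 | 0.60% | 0.55% | 1.96 / 1.78 | 1.31 / 1.19 |
| 0.05 × 0.30 | 1.50% | 1.30% | 4.90 / 4.26 | 3.27 / 2.84 |
| 0.10 × 0.30 | 3.00% | 2.61% | 9.80 / 8.52 | 6.53 / 5.68 |

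The SE is relative to the overall mean, so the overall-base figures are the consistent ones; the other base gives an upper value. With an assumed 100,000 pairs, the SE is 0.447% (CV 1.0) or 0.671% (CV 1.5). The middle case then gives z = 3.35 / 2.92 at CV 1.0 and 2.24 / 1.94 at CV 1.5.

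**Length of stay and intensive care use.** Assume two area types of equal size, overall uptake p = 0.380, an uptake gap g between them, and no true effect. Assume also that matching on the listed variables leaves the area imbalance unchanged. The difference between arms in the share from the high-uptake area is g / [4p(1 − p)] = g / 0.942, so g = 5 points gives 5.3 points. The false difference is this share difference times the difference between areas. Rejection probabilities are two-sided at an assumed 0.05 with 213,381 pairs.

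- Mean outcome: g = 2 points and an area difference of 0.1 SD give 0.0021 SD, significant about 10% of the time. g = 5 points and 0.2 SD give 0.0531 × 0.2 = 0.0106 SD, significant 93% of the time (66% with 100,000 pairs).
- Intensive care use, assumed area rates 12% and 8%: the false odds ratio is 1.010, 1.024, 1.048 and 1.098 for g = 2, 5, 10 and 20 points. At 5 points the rates are 0.08 + 0.04 × 0.5329 = 10.13% and 0.08 + 0.04 × 0.4798 = 9.92%, significant 64% of the time.

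These odds ratios assume that the high-uptake area uses more intensive care; if it uses less, they fall below 1.

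**The case against.** The strongest objection is that the omission is not established. The list in Section 2 is not stated to be exhaustive, the propensity model points to Table 1, and that table is not in the supplied text. A reader might infer that the fitted model left out residence and hospital; the documents do not support this, and the request must be conditional. That part of the objection stands in full.

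Second, the documents give no evidence that uptake or practice varies by area. Bias needs both to vary, and to vary together. This also stands: the mechanism is assumed, and so is its size. Prior-year emergency visits and admissions may pick up some of local practice, though they count use of care and do not locate it.

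Third, a reader might infer that the three resource outcomes mainly measure where patients were treated. The figures do not support this. The false differences are a few percent of expenditure at most and hundredths of an SD or less. Significance at this sample size does not show that an error is material, and it does not separate a small vaccine effect from a small difference in place of care.

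Fourth, the treating hospital is determined at admission, after vaccination. That is a reason to keep hospital out of the propensity model; it does not apply to residence before vaccination.

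What remains is that, on the text as written, nothing after the listed match would detect or correct an area imbalance for these three outcomes.

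**Conclusion.** The concern holds in a conditional form. The listed matching variables contain no region, urbanisation or hospital item, and no adjusted model or area or hospital sensitivity analysis is described for intensive care use, length of stay or expenditure. If uptake and hospital practice both vary by area, and unless Table 1 already contains such a variable, a small bias of unknown direction can enter these outcomes.

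On the assumed inputs it is roughly 0.5 to 3% of expenditure. At the ceiling of 213,381 pairs, the middle case (1.3 to 1.5%) gives z of about 2.8 to 4.9; the smallest case reaches at most 1.96 and is not clearly significant. With fewer pairs all z values fall. The documents do not show that the bias is present, large or in the vaccine's favour, so this is a worthwhile improvement to the analysis and does not invalidate it.

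**What to change.** First state whether Table 1 contains residence or hospital variables. If it does not:

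- Add region and urbanisation of residence, fixed before vaccination, to the propensity model; re-match and re-run the outcomes.
- Report balance between the matched arms on residence and on hospital level, with the matched number of pairs.
- For intensive care use, length of stay and expenditure, add one sensitivity analysis, either within hospital level and region or with a hospital fixed effect. Label it supplementary, because the treating hospital is determined after vaccination.

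The cost is a repeat of the matching and of all seven primary analyses, plus one extra analysis. Exact matching on hospital level and region would lose an unknown number of pairs. No new data collection is needed if the claims hold location and provider fields, which is assumed here.

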- **Categorical variables:** summarized as counts and percentages; compared using the *chi-square test*.
- **Continuous variables:** expressed as mean \pm SD; compared using *independent t-tests*.
- **Risk estimation:** Adjusted odds ratios (ORs) with 95% confidence intervals (CIs) were derived from logistic regression to assess IV effects on infections and mortality.
- **Sensitivity analyses:** stratified by age, sex, comorbidity burden, and fracture type.

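### Do seven unranked primary outcomes with no multiplicity rule call for a family-wise correction?

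*Combined protocol and SAP*

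**What the plan says.** Section 3 (Outcomes) introduces its list with "The primary outcomes, assessed within 30 days postadmission, included". Seven items follow: pneumonia, septicemia, urinary tract infection, use of intensive care, length of stay, total expenditure, and death by 30 days. None is singled out and no order is given.

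Section 5 (Statistical Analysis) names a model for part of that list. Under the risk-estimation item, "Adjusted odds ratios (ORs) with 95% confidence intervals (CIs") "were derived from logistic regression to assess IV effects on infections and mortality". That covers the three infections and mortality, four of the seven.

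Two generic lines come before it. Categorical variables are "summarized as counts and percentages; compared using the *chi-square test", and continuous variables are "compared using *independent t-tests". Neither line names an outcome. They come directly after the propensity-score text, which describes a model "including clinically relevant covariates (Table 1"), so they could describe baseline characteristics, outcomes, or both.

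No significance level, hypothesis, success criterion or multiplicity procedure appears anywhere. Section 2 (Study Design) gives the purpose: the design "was adopted to evaluate the association between influenza vaccination (IV) and clinical outcomes following fracture-related hospitalizations".

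**The concern.** Several endpoints called primary, significance tests named in the analysis section, and silence on multiplicity are together a familiar warning sign. In a confirmatory trial where a win on any one endpoint counts as success, each extra endpoint is another chance to win by luck, and the 5% error rate no longer describes the study as a whole. With no lead outcome, an author could also bring forward whichever of the seven came out significant. Readers would then be told that vaccination before a fracture improves outcomes on evidence weaker than its p-value suggests.

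The usual remedy is cheap: a Holm correction needs only the seven p-values. That makes its absence look like an oversight.

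**Working it through.** The plan states no error rate, power or sample-size figure, so there is nothing of its own to reproduce. The check is how large the inflation would be, and what has to be true for it to arise.

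**Inputs from the document.** Seven primary outcomes (Section 3). Four with a named odds-ratio analysis (Section 5). 213,381 vaccinated and 348,185 unvaccinated patients (Section 2); these add to the stated 561,566, and 1:1 matching allows at most 213,381 pairs.

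**Assumed, because the document is silent.** Two-sided 5% per outcome (suggested by the 95% intervals), all nulls true, tests valid, a common correlation ρ between test statistics, and a rule that any one significant result is a positive finding.

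**Formulas.** With k tests and c = 1.96:

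- Independent tests: 1 − 0.95^k. For k = 4, 1 − 0.8145 = 0.1855. For k = 7, 1 − 0.6983 = 0.3017.
- Correlated tests: 1 − ∫ φ(u) [Φ((c − √ρ·u)/√(1−ρ)) − Φ((−c − √ρ·u)/√(1−ρ))]^k du.
- Only results favouring vaccination (0.025 each): 1 − ∫ φ(u) [Φ((c − √ρ·u)/√(1−ρ))]^k du, which at ρ = 0 is 1 − 0.975^k.

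| Tests | Result that counts | ρ = 0 | ρ = 0.5 | ρ = 0.8 |
|---|---|---|---|---|
| 4 | either direction | 18.5% | 15.6% | 11.4% |
| 7 | either direction | 30.2% | 23.0% | 14.9% |
| 4 | benefit only | 9.6% | 7.8% | 5.7% |
| 7 | benefit only | 16.2% | 11.5% | 7.4% |

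A simulation of 1,000,000 draws at ρ = 0.8 gave 11.4% and 14.9% for the two-sided rows. At ρ = 0.9 those rows fall to 9.4% and 11.4%. Whatever the dependence, the two-sided figures cannot exceed 4 × 0.05 = 20% and 7 × 0.05 = 35%.

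**What the figures need.**

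1. *An any-one rule.* The plan has none. Its stated purpose is to evaluate an association, and its main analysis is labelled as estimation. If each outcome is read from its own interval, its error rate stays at 5% whatever else is reported, and no family-wise rate applies.
2. *Seven tests.* The lower rows for seven outcomes apply only if the chi-square and t-test lines extend to intensive care use, length of stay and expenditure. If those lines describe baseline comparisons, the count is four.
3. *Low correlation.* The 18.5% and 30.2% ends need independence. Intensive care, length of stay and cost arise largely from the same admission, so zero correlation among all seven is an extreme case.

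**What a correction would do.** Holm over seven brings the two-sided rate under the global null to between 4.9% (ρ = 0) and 2.65% (ρ = 0.8). At its strictest step the level is 0.05/7 = 0.0071, and the difference detectable with 80% power grows by (2.6901 + 0.8416)/(1.9600 + 0.8416) = 1.26. Over four outcomes (0.0125) the factor is (2.4977 + 0.8416)/(1.9600 + 0.8416) = 1.19.

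For an assumed 5% event rate and the maximum 213,381 pairs, treating the groups as independent, the detectable difference is 2.8016 × √(2 × 0.05 × 0.95/213,381) = 0.19 percentage points uncorrected, and 3.5317 × the same root = 0.24 corrected. Both are very small, so a correction would probably change few conclusions. It would also leave residual confounding, the larger threat in a non-randomised comparison, exactly where it was.

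**The case for a change.** The best argument for a change is that the plan leaves the any-one reading open. It calls seven outcomes primary, and it names hypothesis tests as well as intervals. A large sample does not help under a true null: a valid 5% test still rejects 5% of the time at any size. Even the most favourable figure in the table, 5.7% for four outcomes counting benefit only, is above its nominal 2.5%. If separate reading is intended, one sentence would say so, and a Holm column costs almost nothing.

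Much of this stands. The silence is real, and so is the lack of a named analysis for three outcomes. But failing to exclude a decision rule is not the same as adopting one, and the same could be said of most observational studies with several outcomes. The missing analyses are a gap that an analyst would fill in the obvious way: a binary comparison for intensive care use and a comparison of means for stay and cost, both already among the methods listed. The plan is also written in the past tense. If the analysis is complete, a correction added now would have to be labelled as such and could not supply pre-specification.

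**Conclusion.** The concern does not call for a change. The facts behind it are right: seven unranked primary outcomes, four with a named odds-ratio analysis, and no significance level or multiplicity rule. The sizes are right as well: 11.4% to 18.5% for four outcomes and 14.9% to 30.2% for seven, or roughly half that if only benefit counts. They rest on an assumed 5% level, all nulls true, assumed correlations from 0.8 to 0 and, decisively, a success rule that the plan nowhere states.

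For a retrospective cohort reporting separate associations with 95% intervals, leaving out family-wise control is a defensible trade-off. It keeps each estimate directly readable and avoids raising the detectable difference by up to 26%, at the price of asking readers to weigh the outcomes one by one. The judgement would differ if the study claimed success on the strength of whichever single outcome reached significance; nothing in the document makes that claim. The unassigned analyses for intensive care use, stay and expenditure are missing detail, not an error.

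### Pneumonia, septicemia or UTI already present on arrival can count as a postfracture infection, because the outcome rule has no onset criterion and UTI has no look-back exclusion

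*Combined protocol and SAP*

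**What the plan says.** Section 2 (Study Design) sets the aim as the association between influenza vaccination and "clinical outcomes following fracture-related hospitalizations". Patients count as vaccinated if they "received IV within 12 months prior to admission".

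Section 3 (Outcomes) lists pneumonia, septicemia and UTI among seven primary outcomes, all "assessed within 30 days postadmission". It gives the ascertainment rule: "Postfracture infections were identified by physician-coded diagnoses during hospitalization or subsequent claims". Its one safeguard on earlier infection is: "Patients with pneumonia or septicemia within 6 months before the fracture were excluded".

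Section 4 (Measures and Definitions) refers to an ICD-9-CM code list in Table S1. That table is not shown in the text available, but it is described as a list of codes, not as a timing rule.

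Section 5 (Statistical Analysis) says that adjusted ORs "were derived from logistic regression to assess IV effects on infections and mortality". Its sensitivity analyses are strata of age, sex, comorbidity burden and fracture type. None concerns when the infection began.

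**The concern.** The outcome is named for infections that follow the fracture, but the rule accepts a qualifying code whatever its onset. The plan states no present-on-admission flag, onset date, minimum lag, diagnosis-position rule or exclusion of admission-day codes. A patient who arrives with a fracture and an undiagnosed UTI or pneumonia is therefore counted as having a postfracture infection.

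Vaccination can precede admission by up to 12 months. The arms may therefore differ in infection already present on arrival, either through a vaccine effect or because vaccinated people are healthier in ways that the matching variables miss. The planned analysis would report such a difference as fewer postfracture infections. If instead the arms do not differ on arrival, the extra events dilute a real effect. Matching on baseline covariates does not correct the timing of an outcome. Three of the seven primary outcomes are affected.

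**Working it through.** **Step 1: the plan's own figures.** The only figure that can be checked is the cohort total: 213,381 vaccinated + 348,185 not vaccinated = 561,566, which agrees with "561,566 patients aged ≥65 years". With 1:1 matching there can be at most 213,381 pairs; the matched number is not stated. The documents give no infection rate and no on-arrival share.

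**Step 2: the rules set against the timeline.**

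| When the infection is first coded | Pneumonia, septicemia | UTI |
|---|---|---|
| In the 6 months before the fracture | Patient excluded | No exclusion stated |
| On arrival, index admission | Counted | Counted |
| Later in the index stay | Counted | Counted |
| After discharge, to day 30 | Counted | Counted |

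The second row is the gap for all three infections. The first row is a further gap for UTI.

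**Step 3: illustration of size.** All inputs here are assumptions. Let p0 be the coded infection risk in the nonvaccinated group, and f the share of those infections present on arrival.

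*Case A: no true postfracture effect, on-arrival OR of 0.7 or 0.8, p0 = 0.05.* The on-arrival risk is a0 = f × p0, with odds o = a0/(1 − a0). In the vaccinated group a1 = OR × o/(1 + OR × o), and the total risk is p1 = a1 + (1 − f) × p0.

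Example with f = 0.3 and OR = 0.7:
- a0 = 0.015 and o = 0.01523
- a1 = 0.01066/1.01066 = 0.01055
- p1 = 0.01055 + 0.035 = 0.04555
- observed OR = (0.04555/0.95445)/(0.05/0.95) = 0.907

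*Case B: true incident RR 0.85, no on-arrival association.* p1 = p0 × [(1 − f) × 0.85 + f × 1.0]. For f = 0.1, p1 = 0.05 × 0.865 = 0.04325, and the OR = (0.04325/0.95675)/(0.05/0.95) = 0.859. The OR for incident infection alone would be about 0.84 to 0.85.

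*Case C: true incident RR 0.85, on-arrival RR 0.7.* As Case B, with 0.7 in place of 1.0.

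| Observed OR, 5% risk | f = 10% | f = 30% | f = 50% |
|---|---|---|---|
| A, on-arrival OR 0.7 | 0.969 | 0.907 | 0.846 |
| A, on-arrival OR 0.8 | 0.979 | 0.938 | 0.897 |
| B, diluted | 0.859 | 0.890 | 0.921 |
| C, exaggerated | 0.828 | 0.797 | 0.766 |

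A coded risk of 2% barely changes these values: at f = 50%, Case A gives 0.848 and 0.899, and Case B gives 0.924.

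**Step 4: how precise a spurious result would look.** Take the maximum of 213,381 per arm and the unpaired standard error of the log OR, √(1/a + 1/b + 1/c + 1/d), where a to d are the four cell counts. For Case A with f = 30% and OR 0.7, there are about 10,669 and 9,719 events. The SE is 0.0144 and the 95% CI is 0.88 to 0.93. With OR 0.8 it is 0.91 to 0.96. Both exclude 1 although no postfracture effect exists. At f = 10% with OR 0.8 the interval is 0.95 to 1.01, which includes 1.

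**The case against.** The best defence is that the cohort was admitted for fracture treatment, that pneumonia and septicemia known before the fracture are already removed, and that every input to the illustration is assumed. If only 10% of coded infections were present on arrival, a null effect would shift by just 0.02 to 0.03. This limits what can be said about size. It does not close the gap, because the exclusion as written stops at the fracture and does not mention UTI.

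Two objections to the obvious remedies also stand.

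- Post-discharge claims do not isolate postfracture infection. They drop infections acquired in hospital, which are plainly postfracture. Unless patients already coded in the index stay are removed, they can also count follow-up of an infection present on arrival. Their time at risk is 30 days minus length of stay, and length of stay is itself a primary outcome.
- Excluding infections seen at the visit leading to admission needs a separate claim for that visit, which the documents do not confirm. Few of these patients may have an infection as principal diagnosis, since they were admitted for a fracture.

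A reader might infer three stronger things that the documents do not support. One is that the bias necessarily favours vaccination; Case B shows the reverse, and nothing in the plan says which case applies. Another is that only an association that persists after discharge deserves the label postfracture infection; a real reduction confined to the hospital stay would fail that test. The third is that infections caused the falls; this is plausible for some patients, but the documents do not address it and the point does not need it.

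**Conclusion.** The concern holds for the three infection outcomes as Table S1 codes them, not for infection in general. The stated rule itself counts infections first diagnosed on arrival, and no planned analysis would show how much they matter. The gap is widest for UTI.

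Under the assumptions above (5% coded risk, 10% to 50% present on arrival), a null postfracture effect could appear as an OR anywhere from 0.98 to 0.85, and a true incident RR of 0.85 could be diluted to an OR between 0.86 and 0.92. Neither the direction nor the size can be settled from the documents. The point limits what the infection results can be said to show; it does not establish that they are wrong. It should be addressed, since most of the remedy uses claims that the plan already draws on.

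**What to change.** Keep the main analysis, state how infections present at admission are handled, and add two analyses.

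1. A sensitivity analysis that excludes patients with the same infection coded on an emergency or outpatient claim up to and including the visit leading to admission, or as principal diagnosis of the index stay where the data record it. Apply the look-back to UTI as well.
2. Infection ORs reported separately for index-stay codes and for first codes after discharge up to day 30, the latter excluding patients already coded in the index stay. Label these as supporting information, and do not make the headline claim conditional on the post-discharge result.

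If the OR changes materially in the first analysis, describe the finding as infection recorded at or after admission, not as prevention of postfracture infection.

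The cost is one extra table and fewer events. The post-discharge analysis omits in-hospital deaths and in-hospital infections, and its time at risk depends on length of stay. The exclusion analysis depends on whether the pre-admission visit has its own claim, which should be confirmed first.

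### UTI is a primary outcome but, unlike pneumonia and septicemia, has no 6-month pre-fracture exclusion, so an earlier UTI coded again can count as a postfracture event

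*Combined protocol and SAP*

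**What the plan says.** Section 3 (Outcomes) lists seven primary outcomes measured over the 30 days after admission. Three are infections: pneumonia, septicemia and "Urinary tract infection". One rule identifies them all: "Postfracture infections were identified by physician-coded diagnoses during hospitalization or subsequent claims". Section 4 (Measures and Definitions) adds that they are "defined by ICD-9-CM diagnostic codes (listed in Table S1"; that table is not in the text supplied.

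The only exclusion for earlier infection follows the identification rule in section 3: "Patients with pneumonia or septicemia within 6 months before the fracture were excluded". UTI is not named there. No section gives a UTI-free look-back, a new-onset rule or a present-on-admission rule, and none explains why UTI is treated differently.

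Two other parts of the plan bear on prior UTI:

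- **Matching.** Section 2 (Study Design) matches on fracture type, comorbidities over 24 months and "Emergency visits and hospitalizations during the prior year", among others. Section 5 (Statistical Analysis) describes the propensity model as "including clinically relevant covariates (Table 1"; that table is also not shown.
- **Sensitivity analyses.** Those in section 5 are patient strata by fracture type, comorbidity burden, sex and age. None concerns prior UTI.

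**The concern.** Removing patients with recent pneumonia or septicemia helps to keep an old infection from being counted as a new one. The same mechanism applies to UTI, because the identification rule accepts any coded diagnosis in the admission or in later claims. Without the exclusion, the UTI OR can mix infections that began before the fracture with those that followed it.

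The effect depends on how carry-over falls between the groups. If it is equal, a true effect is diluted towards 1 and a null result stays null. If it is unequal, the OR can move either way, and an association can appear where there is none. Matching on prior health-care use, and on prior UTI if Table 1 includes it, may make carry-over more equal. It does not stop a carried-over diagnosis from being counted.

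**Working it through.** The plan states no UTI rate, re-coding rate or number of matched pairs, so it has no figure to reproduce. Every rate below is an assumption, chosen to show a range.

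**Inputs**

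- From section 2: 213,381 vaccinated patients, which is an upper limit on the number of 1:1 pairs.
- Assumed: new-UTI risk in the unvaccinated, p0 = 3%, 6% or 10%; true OR = 0.85; carry-over share c = 1%, 2%, 3% or 6%; 50,000 pairs as a smaller alternative.

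**Formulas**

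- Observed risk in a group = p(1 − c) + c. The OR is then taken from the two observed risks.
- Share of counted unvaccinated UTI patients with a carried-over diagnosis = c / observed risk.
- 95% CI factor, treating the groups as unpaired = exp(1.96 × SE), with SE² = (1/n)[1/(r1(1 − r1)) + 1/(r0(1 − r0))], where r1 and r0 are the observed risks and n is the number of pairs.

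**Worked case: p0 = 6%, c = 2% in both groups**

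- True odds in the vaccinated: 0.85 × 0.06/0.94 = 0.05426, so p1 = 0.05426/1.05426 = 0.05146.
- Observed risks: 0.05146 × 0.98 + 0.02 = 0.07043 (vaccinated) and 0.06 × 0.98 + 0.02 = 0.0788 (unvaccinated).
- Observed OR: (0.07043/0.92957)/(0.0788/0.9212) = 0.886.
- Carried-over share: 0.02/0.0788 = 25%.

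**Equal carry-over, true OR 0.85: observed OR (carried-over share in the unvaccinated)**

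| New UTI, unvaccinated | c = 1% | c = 2% | c = 3% | c = 6% |
|---|---|---|---|---|
| 3% | 0.887 (25%) | 0.909 (40%) | 0.924 (51%) | 0.949 (68%) |
| 6% | 0.870 (14%) | 0.886 (25%) | 0.898 (34%) | 0.923 (52%) |
| 10% | 0.862 (9%) | 0.873 (17%) | 0.882 (24%) | 0.903 (39%) |

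The largest shifts need half or more of the counted UTIs to be carried over, so those cells are extreme.

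**Unequal carry-over, no true effect, p0 = 6%**

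| Carry-over ratio, vaccinated/unvaccinated | c = 1% in unvaccinated | c = 2% | c = 3% |
|---|---|---|---|
| 0.8 | 0.97 | 0.95 | 0.93 |
| 0.9 | 0.99 | 0.97 | 0.97 |
| 1.1 | 1.01 | 1.03 | 1.04 |
| 1.2 | 1.03 | 1.05 | 1.07 |

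**Shift against sampling error (equal carry-over)**

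| Case | Shift factor (observed OR/0.85) | CI factor, 50,000 pairs | CI factor, 213,381 pairs |
|---|---|---|---|
| p0 6%, c 1% | 1.024 | 1.052 | 1.025 |
| p0 6%, c 2% | 1.042 | 1.048 | 1.023 |
| p0 6%, c 3% | 1.056 | 1.046 | 1.022 |
| p0 10%, c 2% | 1.027 | 1.040 | 1.019 |
| p0 10%, c 3% | 1.037 | 1.039 | 1.019 |

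Whether the shift exceeds sampling error therefore depends on rates and a pair count that the documents do not give. No general claim can be made.

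**The case against.** The strongest reply is that this is a design choice and not a contradiction. The outcome is a coded UTI within 30 days of admission, and nothing in the plan says it must be a first or UTI-free-interval event. Leaving UTI out of the exclusion also keeps more patients. That is fair, and it is why the point is modest. It does not explain why two of three infections found by the same rule are protected and the third is not; the documents give no reason.

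Second, Tables S1 and 1 are not visible. Table S1 could narrow the UTI codes, and Table 1 could include prior UTI as a matching covariate. This stands as a limit on what can be concluded. Matching on prior UTI would reduce imbalance, the only route to a false association under the null in this model, but carried-over diagnoses would still be counted.

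Third, no consequence is demonstrated: every rate is assumed, and equal carry-over is conservative for a claim of benefit. That also stands. The unequal scenarios assume some imbalance left after matching, and no figure in the documents supports a particular ratio.

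Fourth, it is not stated whether the exclusion defined one cohort for all outcomes or applied outcome by outcome. Either way, UTI has no look-back, so the point is unaffected.

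Finally, the text is written largely in the past tense, so an added analysis may have to be labelled post hoc. This affects the label, not the value of the check.

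**Conclusion.** The concern holds as a point to consider, with medium confidence. As written, the rules let a UTI from before the fracture count as a postfracture event, and the visible matching and sensitivity analyses neither prevent nor test this. It affects one of seven primary outcomes.

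The size and direction of the bias cannot be determined. The illustrative shifts are small at moderate carry-over, and they can be smaller or larger than the CI factor depending on the unstated number of pairs. They rest on the assumed rates, on carry-over being independent of new infection within each group, and, for the dilution figures, on equal carry-over. This is not evidence that the reported UTI OR is biased. It means that an OR for incident UTI cannot be separated from one for any coded UTI.

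**What to change.** Keep the UTI OR as it stands. Add one sensitivity OR that excludes patients with a UTI claim in the 6 months before the fracture, dropping the whole matched pair, and report the two side by side. Define it before it is run, and label it post hoc if the main results are already known.

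Interpretation rule: describe the finding as incident infection only if both ORs lead to the same conclusion. Agreement is necessary but not proof. If they differ, describe the outcome as UTI coded within 30 days of admission. If the asymmetry is kept without this check, state the reason, and say whether Table S1 or Table 1 already deals with prior UTI.

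The cost is one flag and one extra OR. Comorbidities are already "identified from 24-month pre-fracture claims using" diagnostic codes, so the claims are in hand. The downsides are:

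- **Fewer pairs.** With prior-UTI prevalence x and within-pair correlation ρ, the share of pairs lost is 2x − [x² + ρx(1 − x)]. For assumed x = 5%, 10% and 20% this is 9.8%, 19.0% and 36.0% at ρ = 0, and 8.8%, 17.2% and 32.8% at ρ = 0.2.
- **A different population.** The result generalises less well to patients with prior UTI and differs in population from the other ORs.
- **Timing.** Vaccinated patients are those who "received IV within 12 months prior to admission", so part of the 6-month look-back can fall after vaccination.
- **Partial removal.** Infections already present but first coded at admission remain. If half of a 3% equal carry-over was coded before the fracture, the OR at 6% incidence moves only from 0.898 to 0.879, against a true 0.85.
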